5. LIST OF ABBREVIATIONS AND DEFINITIONS OF TERMS

Abbreviation	Definition
AE	Adverse event
ANOVA	Analysis of variance
CFC	Chlorofluorocarbons
CFR	Code of Federal Regulations
CMH	Cochran-Mantel-Haenszel
CNS	Central nervous system
CRF	Case Report Form
DESI	Drug Efficacy Study Implementation
ECG	Electrocardiogram
FDA	Food and Drug Administration
GCP	Good Clinical Practice
GRAS	Generally Recognized as Safe
HCl	Hydrochloride
ICH	International Conference on Harmonization
IND	Investigational New Drug
IRB	Institutional Review Board
ITT	Intent-to-Treat
MedDRA	Medical Dictionary for Regulatory Activities
NF	National Formulary
NRS	Numerical Rating Scale
PI	Principal Investigator
PK	Pharmacokinetics
PPT	Pin Prick Test
PT	Preferred Term
QST	Heat Stimulus Test
SAE	Serious Adverse Event
SOC	System Organs Class
TESS	Treatment Emergent Signs and Symptoms
USP	United States Pharmacopeia

6. ETHICS

6.1 Independent Ethics Committee or Institutional Review Board

This protocol, informed consent form, and any amendments, will be submitted to local ethics committees or institutional review boards (IRBs) for review and approval. A copy of the written approval or vote must be available and sent to the Sponsor before study initiation. Any amendment made to the approved protocol must be forwarded to and approved by the same ethics committees or IRBs before its implementation. Regulatory authority notifications will also be in place and fully documented prior to study start.

The Investigator and appropriate representatives from the Sponsor will sign the protocol to document their willingness to adhere to this protocol and to conduct the study in accordance with the FDA guidelines and the International Conference on Harmonization (ICH) guidelines for Good Clinical Practice (GCP).

6.2 Declaration of Helsinki

This study will be conducted in accordance with the ethical principles that have their origin in the Declaration of Helsinki and consistent with good clinical practice (GCP) as described by the United States Code of Federal Regulations (21CFR parts 50, 54, 56, and 312) and by the ICH Guidelines, effective 17 January 1997.

6.3 Subject Information and Consent

Written informed consent, in accordance with local clinical investigation regulations, must be obtained from the subject (subjects must be 18 years of age or older) prior to participation in the study. The Investigator must provide a description of the study medication (including any potential and possible hazards) and the study procedures to the study subjects. Information must be given both in oral and written form. The subject information provided will be in English, and may not include any language that appears to waive any of the subject's legal rights, or appears to release the Investigator, the Sponsor, the Sponsor's representative, or the institution, from liability or negligence.

The Investigator will provide the prospective subject sufficient time to consider whether or not to participate, minimizing the possibility of coercion or undue influence, and will discuss any questions the subjects may have. The Investigator will explain to the subject that withdrawal from the study is possible at any time without detriment to care. The Investigator will then ask the subject to give consent in writing.

The consent must include acknowledgment that medical records and medical data derived from the study may be forwarded to the Sponsor, to the Sponsor's representative, to the FDA or other regulatory authorities. The informed consent will follow the FDA Regulations and ICH Guidelines, effective 17 January 1997.

7. INTRODUCTION

Cetylite Industries, Inc. (Cetylite) is a small pharmaceutical company based in Pennsauken, New Jersey. The primary product for this company is a local anesthetic spray, Cetacaine® Spray, consisting of a combination of the three active ingredients benzocaine hydrochloride (HCl), tetracaine HCl, and butamben, USP. The company also makes a liquid (solution) formulation with the same constituents (with the exception of a CFC propellant). The product has been grandfathered by the FDA under the DESI review and has been on the market in the US for approximately 60 years. The current indications for Cetacaine® are:

Cetacaine is a topical anesthetic indicated for the production of anesthesia of all accessible mucous membrane except the eyes. Cetacaine® Spray is indicated for use to control pain and gagging. Cetacaine® Spray is indicated to control pain and for use for surgical or endoscopic or other procedures in the ear, nose, mouth, pharynx, larynx, trachea, bronchi, and esophagus.

As a result of the Federal mandate to eliminate CFCs and under current Federal Regulations and exemptions, Cetylite has to reformulate the spray formulation once its supply of CFCs is exhausted (estimated to between 2020 and 2022). Since Cetacaine® is a grandfathered drug that never received an NDA approval; the FDA will now require an NDA for the reformulated product. As part of the recent communication with the FDA, Cetylite has agreed to remove butamben from the product and to reformulate a two-drug combination consisting of 14.0% benzocaine, USP and 2.0% tetracaine HCl, USP delivered without CFCs. The new product is a metered spray designated in this protocol as CTY-5339 Anesthetic Spray (CTY-5339-A).

In Cetylite's most recent correspondence with the FDA in April of 2014, Cetylite outlined its proposed program for the conversion of Cetacaine® Spray containing CFC propellant to a non-CFC containing spray. This letter outlined a proposed new alternate formulation, a proposed animal toxicology study and a clinical program. Since then the CTY-5339 formulation was developed without propellant as a metered dose pump spray. Cetylite has successfully completed a 28-day safety study in rabbits and will file the results of this safety study in their IND Application to initiate human clinical trials.

Summary of Critical Issues and Proposed FDA Questions

One of the key issues for Cetylite is how the development program translates to the final indications for CTY-5339 Anesthetic Spray. The primary use for CTY-5339-A is for the induction of local anesthesia of mucous membranes to suppress the gag reflex during intubation procedures. A secondary, but important, use is for anesthetizing buccal and gingival tissues.

Cetylite's proposed development program to the FDA consisted of the following:

- A 28-day rabbit study using nasal mucosa (completed in April 2016).
- A Phase II Cheek Mucosa study in normal volunteers- partial factorial design.
- A Phase III Nasal Intubation study in normal volunteers- full factorial design.

- A Phase III Gingival Surgery study in patients requiring gingival surgery- full factorial design.

Based on the successful completion of this program, Cetylite anticipates:

- Indications for use in the nose, throat and buccal cavity to suppress the gag reflex and pain sensation.
- Indications for use in all oral mucosa tissues for surgical procedures.

Cetylite's rationale for this development program is:

- Rabbit nasal mucosa is a highly sensitive and representative tissue type in human and provides an acceptable bridge to safety in other mucosal tissues, i.e. throat and buccal cavity.
- The Cheek Mucosa study will serve as the proof of concept study to evaluate the superiority of the combination in comparison to benzocaine alone.
- The Nasal Intubation study will serve as a representative of an airway model:
- The Gingival Surgery study is designed to demonstrate efficacy in a surgical model.

Table 1. Compositions of CTY-5339-A, the Benzocaine-Only Comparator (CTY-5339-CB) and the Vehicle Control (CTY-5339-P)

Ingredient	Grade	CTY-5339- (% w/w)		
		A ^a	CB ^b	P ^c
Benzocaine	USP	14.0	14.0	-
Tetracaine Hydrochloride	USP	2.0	-	-
Dehydrated Alcohol	USP	12.0	12.3	14.4
Polyethylene Glycol 300 (PEG 300)	NF	29.7	30.4	35.5
Propylene Glycol	USP	16.9	17.3	20.2
Purified Water	USP	18.0	18.4	21.5
Benzyl Alcohol	NF	5.0	5.1	6.0
Benzalkonium Chloride Solution (50%)	NF	0.5	0.5	0.5
Saccharin Sodium	USP	1.4	1.4	1.4
Artificial Banana Flavor	Food	0.5	0.5	0.5

^a CTY-5339-A: Active formulation containing both 14.0% benzocaine, USP and 2.0% tetracaine hydrochloride, USP. Note: the term CTY-5339-A is used to designate the active formulation.

^b CTY-5339-CB: comparator formulation containing benzocaine, USP

^c CTY-5339-P: Vehicle formulation containing neither active ingredient

In the proposed human experimental Cheek Mucosal study in healthy volunteers, the CTY-5339-A or comparator CTY-5339-CB formulations will be sprayed onto a

circumscribed approximately one inch diameter area of the cheek. The area will then be tested with pin prick (PPT) and heat (QST) to assess onset and duration of effect. The maximal (total) dose of CTY-5339-A that a subject can receive during this study is 56 mg benzocaine and 8 mg tetracaine HCl. The expectation is that there will be very low systemic exposure of either benzocaine or tetracaine. The doses being used in this study are within the prescribed doses listed on the current Cetacaine® Spray label and are known to be safe doses of these local anesthetics.¹⁻²⁴

The dose of benzocaine and tetracaine being employed in this study are indicated doses on the Cetacaine® label. The PI has examined much higher exposures to benzocaine (80 mg – 200 mg) self-applied by patients to the oral mucous membranes and the offending tooth to treat toothache pain with relatively few minor adverse events recorded (no SAEs and no clinically discernible methemoglobinemia).¹³ Likewise in the development of another product, the PI and his team have dosed subjects with 18 – 36 mg of tetracaine by the intranasal route to obtain maxillary tooth anesthesia with no SAEs reported (again this is 2 – 4 fold greater than the maximum tetracaine exposure on the current study).^{8,10} These three studies were approved by the University of Pennsylvania IRB.

8. RATIONALE, OBJECTIVES, OUTCOMES, AND HYPOTHESIS

8.1 Rationale

The purpose of this study is to evaluate the onset and duration of analgesia in humans when CTY-5339-A is sprayed onto intact cheek mucosal tissue. If this proof-of-concept study is successful, then future studies will evaluate CTY-5339-A in intubation and gingival surgical settings.

8.2 Objectives

The objectives of this study are to evaluate the onset and duration of CTY-5339-A compared to benzocaine only spray (CTY-5339-CB) in a human experimental pain model.

8.3 Outcomes

8.3.1 Primary Outcome Measures

- Duration of anesthesia as measured by PPT for the one spray of CTY-5339-A compared to the one spray of CTY-5339-CB
- Duration of anesthesia as measured by QST Heat for the one spray of CTY-5339-A compared to the one spray of CTY-5339-CB

8.3.2 Secondary Outcome Measures

- Duration of anesthesia as measured by PPT and QST Heat for the two sprays of CTY-5339-A compared to the one spray of CTY-5339-CB plus one spray of CTY-5339-P

- Duration of anesthesia as measured by PPT and QST Heat for the two sprays of CTY-5339-A compared to the one spray of CTY-5339-A
- Onset of anesthesia for PPT and QST Heat
- Percentage of responders for PPT and QST Heat for both onset and duration
- Percentage of responders for PPT and QST Heat at each time point

8.4 Hypothesis

The following hypotheses will be tested to analyze the primary outcomes of the study:

- The null hypothesis that the duration of anesthesia (PPT and QST Heat) for the one spray CTY-5339-A group is the same as the corresponding duration for the CTY-5339-CB one spray group will be tested against the alternative hypothesis that the means are not equal.

The following hypotheses will be tested to analyze the secondary outcomes of the study:

- The null hypothesis that the duration of anesthesia (PPT and QST Heat) for the two spray CTY-5339-A group is the same as the corresponding duration for the CTY-5339-CB one spray plus CTY-5339-P one spray group will be tested against the alternative hypothesis that the means are not equal.
- The null hypothesis that the onset of anesthesia (PPT and QST Heat) for the CTY-5339-A groups is equal to the corresponding onset for CTY-5339-CB group will be tested against the alternative hypothesis that the means are not equal.
- The null hypothesis that the onset time until the first responder event (PPT and QST Heat) for the CTY-5339-A groups is equal to the corresponding onset time until a first responder event for CTY-5339-CB group will be tested against the alternative hypothesis that the event times are not equal.
- The null hypothesis that the duration time until the first non-responder event (QST and PPT) for the CTY-5339-A groups is equal to the corresponding duration time until the first non-responder event for CTY-5339-CB group will be tested against the alternative hypothesis that the event times are not equal.

The predicted outcome is that CTY-5339-A when locally applied to cheek mucosal tissue in the mouth will have an onset comparable to the fastest constituent, benzocaine, and a prolonged effect comparable to the longest acting constituent, tetracaine, of the combination product. The study also is designed to demonstrate that both the CTY-5339-A one and two-spray dosages are safe. (The assumption is made that benzocaine has a faster onset of action than tetracaine HCl.)

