9. SUMMARY OF STUDY DESIGN

This is a single-dose, double-blind and single-center study with an active control treatment. All subjects will remain at the study center for each of the two 60 minute test sessions. The volunteer subjects will be tested at two different test sessions separated by 4-14 days and serve as their own control.

The study will include 76 subjects with 60-minute evaluations at each test session.

At each session, a circular area of approximately 1 inch in diameter will be isolated on one side of the cheek. Each session will use a different side of the cheek. The possible sequences of treatments at the two sessions are:

Session 1		Session 2	
Formulation	Sprays	Formulations	Sprays
CTY-5339-A	1	CTY-5339-CB	1
CTY-5339-A	2	CTY-5339-CB	1
CTY-5339-CB	1	CTY-5339-A	1
CTY-5339-CB	1	CTY-5339-A	2

(To maintain double-blind conditions, the CTY-5339-CB subjects in two spray sequences will also receive one spray with the vehicle control (CTY-5339-P) just outside the circumscribed area. A third party not involved with evaluating subjects will administer the drug.)

For PPT, evaluations will be done at 1-minute intervals following drug administration for the first 5 minutes to capture onset of anesthesia. Starting at 5 minutes after drug administration, both PPT and QST will be done at 5-minute intervals up to the one hour time point. Once onset has occurred, if there is no analgesia at two consecutive evaluation time points (from 10 minutes onward), the session will be discontinued. In addition, if onset of analgesia has not occurred by 10 minutes post dose, the subject will be considered a treatment failure and no further assessments will be made.

PPT: The PPT will be assessed, using a 90-mm, 26-gauge pencil-point spinal needle (Polymedic or equivalent; Temena S.A., Bondy, France or its equivalent). At each post dosing time point, PPT will be assessed in 3 repetitions on the non-treated site using a 0-10 Numerical Rating Scale (NRS) with "0" as no pain and "10" as severe pain. PPT will then be assessed in 3 repetitions on the treated site. These assessments will be compared to the contra-lateral, non-treated site as "No pain", "Less Pain" or "Similar/More Pain". "No Pain" or "Less Pain" at an application site will be recorded as presence of analgesia/anesthesia ("Responder").

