QST: The heat stimuli are delivered in 3 repetitions, with inter-stimulus intervals of 30s. The basal thermode temperature is set at a comfortable 35°C. The rate at which the thermode heats up is set at 0.5°C/s, while the rate at which it cools down is set at 8°C/s. The maximum thermode temperature is set at 51°C. The first stimulus is disregarded and the remaining two stimuli are averaged for data analysis. In situations where a maximal analgesia/anesthesia effect is demonstrated in the initial two repetitions, the QST test will not be repeated for the third repetition and the data will be recorded as maximal effect (51°C) based on the first two repetitions.

Heat sensation threshold will be defined as the temperature at which the subjects first start to feel tingling, warmth, heat, or pain. All tests will be done near the center of the circumscribed area, but in a different place at each evaluation time point. For QST, the first time point after Baseline will begin at 5 minutes after drug administration. Subjects will have a hand held mouse that turns off the heat probe when they first start to feel tingling, warmth, heat, or pain. At the maximum heat level of 51° C, the heat probe turns off automatically. With a brief exposure at 51° C, there is no damage to the mucosal tissue.²⁵

Randomization: A randomization code will determine in which circumscribed area each treatment is administered (left or right cheek). Immediately prior to beginning each 60 minute test session, both the contra-lateral cheek and the cheek to be dosed will be evaluated with the PPT. For QST, the screening assessments will be performed on both cheeks, while during each treatment Session, at Baseline and all post-dosing time points, assessments will be performed on the treated cheek only.

Subjects retain the right to withdraw from the study at any time.

The PPT and QST tests will be done near the center of each evaluation area but in a different place at each evaluation time point. For PPT, the non-treated control cheek will always be tested before the treated area. The testing will be done in the following order where applicable: PPT and then QST.

A safety phone follow-up call will occur 3 days (± 1 day) after the Session 1 and 15 days (± 2 days) following Session 2.

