13.5 Statistical Methods for Efficacy Evaluations

The primary efficacy analyses will be based on Modified Intent-to-Treat Population. The key comparisons will include:

1. CTY-5339-A, one spray versus CTY-5339-CB, one spray

The co-primary efficacy variables are duration of effect as measured by PPT and QST Heat. Duration of effect is defined as the time (in minutes) from onset to treatment failure (*i.e.*, for PPT, an assessment of “Same/More” pain, and for QST, the average heat temperature is greater than the average heat temperature at Baseline (non-treated cheek), up to the 60-minute time point (at two consecutive time points). For those discontinuing from the study for any other reason, the time to treatment failure will be censored at the last assessment time.

The secondary efficacy variables include:

- Duration of effect (PPT and QST) for CTY-5339A two sprays versus CTY-5339-CB, one spray plus CTY-5339-P one spray

- Duration of effect (PPT and QST) for CTY-5339A two sprays versus CTY-5339-A one spray
- Onset of anesthesia in minutes for PPT and QST Heat
- Percentage of responders at each time point for PPT and QST Heat for both onset and duration

Continuous variables will be analyzed via an ANOVA model with treatment effects at each of assessed time points. Pairwise comparisons for variables related to percentages will be analyzed via chi square tests. The 95% confidence intervals of the treatment differences will be presented using normal approximation with continuity correction, if appropriate. Pairwise comparisons for time-to-event related variables will be analyzed via a log rank model with treatment effects. Median time to event will be estimated and the 95% confidence intervals for the median will be presented, if appropriate.

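### Onset is tested both as a mean and as a time to event with neither given precedence, and no rule says how a session without onset by 10 minutes enters the mean

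*Combined protocol and SAP*

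**What the plan says.** Section 8.4 lists four secondary hypotheses. The second concerns mean onset for PPT and QST Heat, CTY-5339-A groups against CTY-5339-CB: "corresponding onset for CTY-5339-CB group will be tested against the alternative hypothesis that the means are not equal". The third concerns the same measures and groups as a time to event: "The null hypothesis that the onset time until the first responder event (PPT and QST Heat) for the CTY-5339-A groups" is set equal to the CTY-5339-CB value, and the "corresponding onset time until a first responder event for CTY-5339-CB group will be tested" against unequal event times. The section does not say which of the two decides the onset question.

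Section 13.5 lists onset in minutes among the secondary variables. It then gives a method by type of variable. For one type, "Continuous variables will be analyzed via an ANOVA model with treatment effects at each of assessed time points". For another, "Pairwise comparisons for time-to-event related variables will be analyzed via a log rank model with treatment effects", with median times and confidence intervals. Percentages go to chi-square tests. Onset is not assigned to a type. The synopsis adds ANOVA with pairwise t-tests for the treatment comparisons, and says that the share of subjects who have onset will be compared between treatments.

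Section 9 fixes the follow-up for onset: "if onset of analgesia has not occurred by 10 minutes post dose, the subject will be considered a treatment failure and no further assessments" are made. PPT is read each minute to 5 minutes and then every 5 minutes. QST starts later: "For QST, the first time point after Baseline will begin at 5 minutes after drug administration".

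**The concern.** A session with no onset by 10 minutes is an observation about onset: it was slow or it failed. A time-to-event analysis can hold that information. A mean of onset minutes cannot, unless someone assigns a value. If the mean is taken over recorded onset times, sessions are selected on an outcome that occurs after dosing. The slower product loses more of its slow sessions, so its mean moves towards that of the faster one. A product that more often fails to numb, but is equally quick when it works, shows no difference at all.

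The direction matters because Sections 3 and 8.4 predict that CTY-5339-A will have an onset comparable to benzocaine. A test that shrinks onset differences will tend to be non-significant, and that result would appear to support the prediction. With two prespecified onset tests and no precedence, the report could show one that finds a difference and one that does not, and the plan would not say which to believe.

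**Working it through.** **1. Is there any rule that gives a no-onset session a value?**

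- Section 13.2: secondary analyses use the ITT population (randomized, dosed, with a Baseline). This keeps the subject in the population but supplies no onset time.
- Section 13.4.1: before onset, LOCF fills missing readings. It carries non-response forward and creates no onset.
- Section 13.5: the only censoring rule is for time to treatment failure, which is the duration variable.

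So no rule gives a value for the mean test, and none states the censoring for the onset log rank. No passage says that such sessions are dropped, either.

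**2. Inputs.** From the documents: 38 exposures per CTY-5339-A regimen (76/2), two-sided 0.05, PPT readings at 1, 2, 3, 4, 5 and 10 minutes within the onset window. The sample size of 76 has no effect size, SD or power behind it, so there is no planned power to reproduce. Onset latencies and rates are not given, so those below are assumptions.

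**3. How far the mean shrinks.** For an exponential latency with mean m, let e = exp(-10/m). The share with onset by 10 minutes is 1 - e, and the mean among those sessions is m - 10e/(1 - e).

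- m = 4: e = 0.082, share 92%, mean 4 - 0.82/0.918 = 3.11.
- m = 8: e = 0.287, share 71%, mean 8 - 2.87/0.713 = 3.98.

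A true gap of 4 minutes becomes 3.98 - 3.11 = 0.87 minutes. On the PPT reading grid the simulated means are 5.30 and 4.19, a gap of about 1.1.

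**4. Power by simulation**, 38 v 38 independent sessions. Log rank censors no-onset sessions at 10 minutes.

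| PPT scenario (CTY-5339-A v CTY-5339-CB) | Mean, sessions with onset | Log rank | Chi-square on share with onset |
|---|---|---|---|
| Exponential, 8 v 4 min | 22% | 78% | 67% |
| Exponential, 4 v 2 min | 59% | 81% | 33% |
| Exponential, 12 v 4 min | 33% | 98% | 96% |
| Same speed, 70% v 95% ever numb | about 5% | 67-75% | 77-85% |

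The ranges in the last row cover different assumed latencies. Separate runs of the 8 v 4 row, including one with a within-subject correlation of 0.4, gave 21-24% for the mean test and 76-82% for log rank.

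**5. Sensitivity to the assumptions**, 8 v 4 minutes:

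- No-onset sessions scored as 10 minutes, exponential: the mean test rises to about 64%.
- Gamma latencies with shape 3 and the same means: mean among sessions with onset 86%, log rank nearly 100%.
- When nearly every session has onset in time (exponential, 3 v 2 minutes, correlation 0.4), the loss is small: 25% against 36%.

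**6. How often the two tests would disagree.** With exponential latencies of 8 v 4 minutes and correlation 0.4, the mean test was non-significant while log rank was significant in 60% of runs. In the 70% v 95% case it was 62-71%.

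**The case against.** A reader might infer that the plan as a whole compares only sessions that worked, so that a slow or unreliable product would pass unnoticed. The documents do not support that. The hypothesis immediately after the mean-onset one is a time-to-event test, Section 13.5 provides log rank and medians, and the percentage with onset is to be compared. In the case that hurts the mean test most (70% v 95% ever numb), the planned chi-square has 77-85% power, above log rank. A less reliable product would probably show up somewhere in the report.

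The exclusion is also an inference. Nothing stops the statistician from assigning a value, and scoring 10 minutes recovers most of the power. Exponential latencies have a long tail past 10 minutes, which makes the loss look large; with a tighter distribution the mean test performs well. Onset is secondary, and the success rule in Section 13.6 concerns duration only.

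All of this stands and limits the size of the point. It does not remove it. The mean-onset hypothesis is still written into Section 8.4 with no defined value for a no-onset session, and any imputed value would be arbitrary because the true time is unknown. Chi-square catches unreliability but is weak on slowness: 33% at 4 v 2 minutes, against 81% for log rank.

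**Conclusion.** The point holds for the mean test of onset, not for the planned onset analyses taken together. Section 8.4 states two tests of one variable without precedence, and the mean version needs either selection on a post-dosing outcome or an imputed value that the plan does not give. If only recorded onset times are used, the test has power near its 5% level against lower reliability and reduced power against slowness. The loss ranges from large (22% against 78%) to modest (86% against nearly 100%) for the same 8 v 4 minute difference, depending on the shape assumed for latency. The documents give no latency data to choose between these.

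A separate limit applies to every onset test here: no margin defines comparable onset, so a non-significant result, log rank included, does not show it. The change should be made, but the primary conclusion on duration does not depend on it.

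**What to change.** - Section 8.4: delete the mean-onset hypothesis and keep time to first responder event as the only onset test.
- Section 13.5: list onset as a time-to-event variable, with every dosed session included and sessions without onset censored at their 10-minute reading.
- Report the percentage with onset by 10 minutes beside the log rank result. Label any mean as descriptive, among sessions with onset only.
- State that a non-significant onset test will not be read as showing comparable onset.

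Cost: wording only, with no new data, visits or subjects. The onset result may look less favourable to the prediction of comparable onset.
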